7.4. Adverse Events and Serious Adverse Events

The occurrence of an adverse event (AE) or serious adverse event (SAE) may come to the attention of study personnel during filling of the eCRF, treatments/other medical procedures or upon review by a study monitor.

7.4.1. Adverse events (AE)

AE DEFINITION

Adverse event means any untoward medical occurrence associated with the use of an intervention in humans, whether or not considered intervention-related. An AE can therefore be any unfavorable and unintended sign (including an abnormal laboratory finding), symptom, or disease temporally associated with the use of a medicinal (investigational) product, whether or not related to the medicinal (investigational) product.

NOTE 1- This includes any event that is a result of a use error or intentional misuse.

Subject: smART Plus Comparative Study Protocol - Beilinson

NOTE 2: This includes events related to the procedures involved (any procedure in the clinical investigation plan).

NOTE 3: For users or other persons this is restricted to events related to the investigational medical device.

AE CLASSIFICATION AND REPORTING

Group A- Interventional Device

All AEs will be recorded on the adverse events page of the eCRF. AEs will be recorded after the subject (or delegate) has signed the informed consent and throughout the study. Any medical condition that is present at the time that the participant is screened will be considered as baseline and not reported as an AE. However, if the study participant's condition deteriorates at any time during the study, it will be recorded as an AE. AE reporting and documentation will be discontinued, at the end of the study, immediately after feeding tube removal.

Information to be collected includes event description, time of onset, clinician's assessment of severity, relationship to study product (assessed only by those with the training and authority to make a diagnosis), and time of resolution/stabilization of the event. All AEs occurring during the study must be documented appropriately regardless of relationship. All AEs will be followed to adequate resolution.

Severity and relationship to study device will be assigned by the investigator as described below.

All adverse events will be graded for severity as follows:

- **Mild:** Events, sign or symptom, usually transient, requiring minimal or no special treatment and generally not interfering with participant's usual activities.
- **Moderate:** Events, sign or symptom, which may be ameliorated by simple therapeutic measures; yet, may interfere with usual activity.
- **Severe:** Events, sign or symptom that are intense or debilitating and that interfere with usual activities. Recovery is usually aided by therapeutic measures.

All adverse events (AEs) must have their relationship to study intervention assessed by the clinician who examines and evaluates the participant based on temporal relationship and his/her clinical judgment. The degree of certainty about causality will be graded using the categories below.

- **Probably related:** Follows a reasonable temporal sequence from study device delivery/retrieval, and cannot be reasonably explained by known characteristics of the subject's clinical data or the surgical procedure applied.
- **Possible related:** Follows a reasonable temporal sequence from study device delivery/retrieval but could have been produced by the subject's clinical state or by the surgical procedures regardless of the study device.
- **Not related:** No relationship to study device activation is perceived.

Group B- Control Group

Subject: smART Plus Comparative Study Protocol - Beilinson

AEs recorded for group B should include only related or could affect (according to PI decision) the patient's medical condition that related to urine, feeding, GRV and REE.

7.4.2.Serious Adverse Events (SAE)

SAE DEFINITION

A "serious Adverse Event is an adverse event that:

- a) led to a death,
- b) led to a serious deterioration in health that either:
 - 1) resulted in a life-threatening illness or injury, or
 - 2) resulted in a permanent impairment of a body structure or a body function, or
 - 3) required in-patient hospitalization or prolongation of existing hospitalization, or
 - 4) resulted in medical or surgical intervention to prevent life threatening illness or injury or permanent impairment to a body structure or a body function.
- c) led to fetal distress, fetal death or a congenital abnormality or birth defect.

NOTE 1: This includes device deficiencies that might have led to a serious adverse event if a) suitable action had not been taken or b) intervention had not been made or c) if circumstances had been less fortunate. These are handled under the SAE reporting system.

NOTE 2: A planned hospitalization for pre-existing condition, or a procedure required by the Clinical Investigation Plan, without a serious deterioration in health, is not considered to be a serious adverse event.

SAE REPORTING

Due to the complex clinical status of the patients a very large number of AEs and SAEs occur; therefore, **only device related SAEs will be reported to the IRB / local ethic committee**.

This is in line with information provided in FDA guidance document "Guidance for Clinical Investigators, Sponsors, and IRBs Adverse Event Reporting to IRBs - Improving Human Subject Protection". Per the guidance and the IDE regulation, reportable events to the IRB are: "any serious adverse effect on health or safety or any life-threatening problem or death caused by, or associated with, a device, if that effect, problem, or death was not previously identified in nature, severity, or degree of incidence in the investigational plan or application (including a supplementary plan or application), or any other unanticipated serious problem associated with a device that relates to the rights, safety, or welfare of subjects."

The guidance further states: "Sponsors can assess the implications and significance of AE reports promptly and are required to report serious, unexpected events associated with the use of a drug or device, including analyses of such events, to investigators and to FDA. In addition, sponsors are required to report analyses of unexpected adverse device experiences to IRBs."

The study investigator shall complete an Unanticipated Adverse Device Effect Form and submit to the study sponsor and to the reviewing Institutional Review Board (IRB) as soon as

Subject: smART Plus Comparative Study Protocol - Beilinson

possible, but in no event later than 10 working days after the investigator first learns of the effect. The study sponsor is responsible for conducting an evaluation of an unanticipated adverse device effect and shall report the results of such evaluation to the Food and Drug Administration (FDA) and to all reviewing IRBs and participating investigators within 10 working days after the sponsor first receives notice of the effect. Thereafter, the sponsor shall submit such additional reports concerning the effect as FDA requests.

Accompanying documentation, such as copies of hospital case reports, autopsy report, and other documents when applicable, should be sent to the sponsor as soon as they are available.

Subjects who have had an SAE must be followed clinically until all parameters (including laboratory) either have returned to normal or are stabilized.

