1.2.2. Neso-gastro (ng) tube positioning

Although generally safe and effective, NG tubes are usually inserted blindly at the bedside and there is a wide spectrum of known complications associated with feeding tube placement. The most common serious complication is misplacement of the feeding tube into the bronchial tree with resulting pneumonitis, pneumonia, and/or pneumothorax if not recognized. This is reported to occur in 2.4%–3.2% of nasogastric insertions. The rate of migration of jejunal placement back to the duodenum or stomach is 27%–42%⁷.

It is estimated that approximately 1.2 million feeding tubes are placed each year in the United States alone. If these tubes were placed blindly this would translate to 3,600 to 8,400 pulmonary injuries, and 1,200 to 3,600 deaths in the United States each year.

Positioning complications also occur throughout the duration of the use of the tube. Movement of the distal tip of the feeding tube occurs even when the NG tube is taped in place. This is most likely to occur with soft, small-bore NG tubes. Malpositioning of the indwelling tube may result in injury or aspiration.

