4.1. Inclusion Criteria

- 4.1.1. Males and females 18 years or older
- 4.1.2. Patients that have already been admitted to ICU (admitted to the ICU for no more than 48 hours before enrollment)
- 4.1.3. Expected to be ventilated at least 48 hours after enrollments.
- 4.1.4. Patient requires enteral feeding (by naso/oro-gastric feeding tube)

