7.1. Participant Discontinuation/Withdrawal from The Study

Each subject (or delegate) will be informed of his/her right to withdraw from the study at any time and for any reason. The Investigator may withdraw a subject from the study at any time if he considers that remaining in the study compromises the subject's health.

Additional criteria for discontinuation/withdrawal:

- The insertion of the feeding tube has failed after 3 attempts in each nostril
- Disease progression which requires discontinuation of the study intervention
- If the participant meets an exclusion criterion (either newly developed or not previously recognized) that precludes further study participation.

In the event a subject discontinuation/withdraws from the study the following procedures will be observed:

- The reasons for any subject discontinuation/withdrawal will be recorded on the study completion form of the eCRF.
- The investigator will inform the sponsor of the subject's early withdrawal for any reason.
- If withdrawal is caused by an adverse event that the investigator considers may be related to the device, it will be reported to the IRB and to the Sponsor.

Subjects who signed the informed consent form and are randomized but do not receive the study intervention are considered screen failures and may be replaced. Subjects who sign the informed consent form, and are randomized and receive the study intervention, and subsequently withdraw, or are withdrawn or discontinued from the study may also be replaced.

 ART MEDICAL PATIENT SAFETY TECHNOLOGY	Number: CRO-C-2822	Date issued: 01-Mar-2021
	Rev.06	Page 25 of 35

Subject: smART Plus Comparative Study Protocol - Beilinson

In addition, this study may be temporarily suspended or prematurely terminated if there is sufficient reasonable cause.

Circumstances that may warrant termination or suspension include according to the PI decision, but are not limited to:

- Determination of unexpected, significant, or unacceptable risk to participants
- Demonstration of efficacy that would warrant stopping
- Insufficient compliance to protocol requirements
- Data that are not sufficiently complete and/or evaluable
- Determination that the primary endpoint has been met
- Determination of futility

Study may resume once concerns about safety, protocol compliance, and data quality are addressed, and satisfy the sponsor, IRB and/or Food and Drug Administration (FDA).

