7.4.3. Expected / anticipated adverse events

Expected/anticipated adverse events are AEs that are known to occur for the study intervention being studied and should be collected and recorded in the study eCRF (as other AEs).

Anticipated adverse events associated with the insertion and presence of feeding tubes include:

- Inconvenient sensation in the neck or chest during or after insertion of the feeding tube and during feeding.
- Nasal bleeding during insertion attempt of the tube.
- Difficulty in breathing, coughing and chest pain due to insertion of the tube, mistakenly, into the trachea.
- Difficulty in swallowing due to the presence of the feeding tube.
- Nausea and vomiting
- Pneumothorax

Anticipated adverse events associated with feeding are:

- Abdominal discomfort and pain
- Abdominal bloating
- Diarrhea

The study PI will be responsible for determining whether an adverse event (AE) is expected or unexpected. An AE will be considered unexpected if the nature, severity, or frequency of the event is not consistent with the risk information previously described for the study intervention.

 ART MEDICAL <small>PATIENT SAFETY TECHNOLOGY</small>	Number: CRO-C-2822	Date issued: 01-Mar-2021
	Rev.06	Page 29 of 35

Subject: smART Plus Comparative Study Protocol - Beilinson

Expected/anticipated adverse events will be reported in the study eCRF and marked as “Expected/anticipated adverse events”.

8. Monitoring Plan

Monitoring functions shall be performed in compliance with Good Clinical Practices, EN ISO 14155:2011, as outlined in 21CFR§821.43(d) and 21CFR§812.46, and according to any other local regulations.

ART MEDICAL will appoint a Clinical Monitor for this study. The Clinical Monitor should be qualified by training and experience to oversee the conduct of the study. The Clinical Monitor's responsibilities include maintaining regular contact with the investigational site, through telephone contact and on-site visits, to ensure that: 1) the study protocol is followed; 2) that complete, timely, and accurate data are gathered; 3) that problems with inconsistent and incomplete data are addressed; and 4) that complications and Unanticipated Adverse Device Effects are reported to the Sponsor.

The investigational site will provide to the monitor direct access to the trial related source data/documents, and reports for the purpose of monitoring and auditing by the sponsor, and inspection by local and regulatory authorities.

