- The two-sample T-test or Non-parametric Wilcoxon-Mann-Whitney Rank sum test for independent samples (as is appropriate) will be applied for testing the statistical significance of the difference in the estimated nursing time that was expended for GRV activities, and the amounts of GRV removed from the patient between the study groups.
- Convenience of use of the system and the user interface scores (by subjective staff questionnaire) will be summarized in an appropriate table by study group
- The two-sample T-test or Non-parametric Wilcoxon-Mann-Whitney Rank sum test for independent samples (as is appropriate) will be applied for testing the statistical significance of the difference in the assessment of urine flow monitoring related to patient condition and usability between the study groups.
- The two-sample T-test or Non-parametric Wilcoxon-Mann-Whitney Rank sum test for independent samples (as is appropriate) will be applied for testing the statistical significance of the difference in ICU length of stay (measured from admission to ICU until the decision to discharge is ordered) between the study groups.
- Chi-square test or Fisher's Exact test (as is appropriate) will be applied for testing the statistical significance of the difference in percent of subjects experiencing Ventilation associated events between the study groups.

9.2.5 Safety:

Adverse events will be coded using the Medical Dictionary for Regulatory Activities (MedDRA, most updated version) terminology and presented in tables by System Organ Class (SOC) and Preferred Term (PT).

Subject: smART Plus Comparative Study Protocol - Beilinson

AE data will be listed individually and summarized by SOC and by PT within a system organ class for each study group.

Frequency of TEAEs (Treatment-Emergent Adverse Events) and device-related adverse events will be summarized in tables by SOC, PT and study group and by seriousness.

Chi-square test or Fisher's Exact test (as is appropriate) will be applied for testing the statistical significance of the difference in percent of subjects experienced any AE, drug-related AE and SAE between the study groups.

Concomitant medications entered into the database will be coded using the World Health Organization (WHO) Drug Reference List, which employs the Anatomical Therapeutic Chemical classification system.

10. Regulatory, Ethical, and Study Oversight Considerations

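### smART+ insertion harms fall inside the AE window, but control insertion harms may go unrecorded, so the between-arm AE and SAE tests mix insertion with safety in use

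*Combined protocol and SAP*

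**What the plan says.** Section 7.4.1 gives each arm its own AE rules. Under the group A heading, "AEs will be recorded after the subject (or delegate) has signed the informed consent and throughout the study", and "All AEs occurring during the study must be documented appropriately regardless of relationship". The baseline rule stands under the same heading: "Any medical condition that is present at the time that the participant is screened will be considered as baseline and not reported as an AE". The group B paragraph has no start rule and no baseline rule. It limits recording to events that the investigator links to feeding, gastric residual volume, urine or energy expenditure. The schedule in 5.5, by contrast, marks adverse events for both arms at every stage, without that limit.

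Group A's tube is placed after consent (5.2.1, 5.2.3). Group B uses the hospital's ordinary tubes (5.3.3), and section 5.3 contains no insertion step. Eligible patients are "admitted to the ICU for no more than 48 hours before enrollment" (4.1), and 4.2 does not exclude a patient who already has a tube.

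Section 7.4.3 lists insertion and tube-presence events, such as "Nasal bleeding during insertion attempt of the tube", separately from feeding events. Section 1.2.2 gives the only insertion-harm rate, for misplacement into the bronchial tree: "This is reported to occur in 2.4%–3.2% of nasogastric insertions". Section 7.1 makes it a withdrawal criterion that "The insertion of the feeding tube has failed after 3 attempts in each nostril". Section 9.2.5 then provides for "testing the statistical significance of the difference in percent of subjects experienced any AE, drug-related AE and SAE between the study groups", with no split between insertion and later use.

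**The concern.** A group A patient who reaches placement has an insertion while AEs are being recorded. A control patient may have had the only insertion before consent, or may have one during the study whose harms fall outside the group B topics. Two equally safe tubes could then show more nose bleeds, tracheal placements or pneumothoraces in group A. That excess could be taken as evidence about the device in use, although part of it comes from the extra insertion and part from unequal recording. By the same route, a true placement advantage of the sensor-guided tube, which section 1.8.2 claims as a benefit, could be masked. None of the data items listed in 5.2.8 or 5.3.5 is tube status at randomisation. The eCRF itself is not in the documents, so whether it holds such a field cannot be checked.

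**Working it through.** The plan states no AE rate, no power for the safety tests and no share of controls with a tube, so there is no planned figure to reproduce. The check has three steps.

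**1. Which insertions can be counted**

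| Insertion | Recorded as an AE source? | Basis |
|---|---|---|
| Hospital tube before consent, either arm | No | Recording opens at consent; nothing provides for earlier collection |
| smART+ tube, group A | Yes, all AEs | 5.2.1, 5.2.3, 7.4.1 |
| Hospital tube after consent, group B | Unclear | Group B topics omit insertion; the schedule row has no such limit |

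Harms from before consent are left out of both arms. The difference comes from the second and third rows.

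**2. Expected misplacements**

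Inputs: q = 2.4% to 3.2% (1.2.2) and n = 100 per arm (9.1). The share f of control insertion harms not counted, for either reason, is an assumption. Assume one insertion per patient and equally safe tubes.

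- Group A: 100 × q = 2.4 to 3.2.
- Group B: 100 × (1 − f) × q. This gives 2.16 to 2.88 at f = 10%, 1.2 to 1.6 at f = 50%, and 0 at f = 100%.

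Even 3 versus 0 of 100 gives a two-sided Fisher p of 2 × (100 × 99 × 98)/(200 × 199 × 198) = 0.25.

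**3. Effect on the any-AE test**

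Let b be the risk of any other recorded AE, assumed equal in both arms so as to isolate insertion. Then:

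- P(AE, group A) = 1 − (1 − b)(1 − q)
- P(AE, group B) = 1 − (1 − b)(1 − q(1 − f))
- Gap = (1 − b) × q × f, at most 0.95 × 0.032 × 1 = 3.0 points at b = 5%.

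The table gives the probability of rejection at the two-sided 0.05 level, by exact binomial enumeration, with no other difference between arms. Chi-square is uncorrected; Fisher is in brackets.

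| b (assumed) | q = 2.4% to 3.2%, f = 1 | q = 20% (assumed), f = 1 |
|---|---|---|
| 5% | 9.7% to 13.5% (5.8% to 8.5%) | 98.2% (97.1%) |
| 20% | 6.4% to 7.4% (4.3% to 5.0%) | 71.9% (66.4%) |
| 50% | 5.9% to 6.2% (4.3% to 4.5%) | 31.0% (26.1%) |
| 80% | 5.2% to 5.3% (3.3% to 3.4%) | 11.6% (8.3%) |

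At f = 0.5 and q = 2.4% to 3.2%, chi-square rejection is 5.2% to 6.9% over all four values of b. With f = 0 it is 5.0% to 5.6%. The 20% column is illustrative: the documents give no rate for nasal bleeding or for insertion harms in total.

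**The case against.** A reader might infer that the tests are biased against smART+: every group A insertion is counted, while the baseline rule strikes out those of controls who arrive with a tube. The documents do not support that, for four reasons.

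- The baseline sentence belongs to the group A rules. What can lose control insertion harms is the start of collection at consent and the narrow group B scope.
- No passage says that any control arrives with a tube. Section 5.3.3 places the group B feeding programme after the energy-expenditure step, which is compatible with a tube placed after enrolment.
- Not every group A insertion need be counted. Failed insertion can lead to withdrawal, and 7.1 treats randomised patients who do not receive the intervention as replaceable screen failures. For screen failures, 4.5 asks only for serious events. This could remove insertion harms from group A, so the net direction is not settled.
- If assignment to smART+ brings an extra insertion, its harm is an effect of assignment. A randomised comparison should include it.

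A further objection is that the events can already be separated. AEs carry onset time and relatedness, are tabulated by preferred term, and are flagged when expected; the safety endpoint in 2.2 is device-related events. This stands for group A, where the events are recorded. It cannot recover control events that were never entered, and 9.2.5 still tests any AE and SAE between arms.

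The objection on size also stands. Section 7.4.2 expects very many AEs and SAEs in these patients, which points towards the lower rows of the table, at least for group A.

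**Conclusion.** The point holds in limited form. Insertion harms of the smART+ tube are inside the AE window, while those of control tubes may be missed because of timing, recording scope or both. The any-AE and SAE comparisons thus combine three things: a real effect of the extra insertion, unequal recording of insertion harms, and safety in use.

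At the only rate in the documents the consequence is small. Chi-square rejection is at most 13.5%, and that needs all control insertion harms uncounted and other AEs at only 5%. It becomes large only if insertion harms in total are common and other recorded AEs are rare. These figures rest on assumed values of f and b, on b being equal in the arms, and on one insertion per patient. In practice b is not recorded equally, because the group B limit drops every event outside its four topics. That wider gap is the larger weakness of these tests; equal scope alone would still leave insertions before consent uncounted.

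A reader might also conclude that the safety statement should rest only on events after placement. That does not follow: group A's clock would start at a successful placement after randomisation, while a control with a tube already in place would start at randomisation.

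**What to change.** 1. Name tube-insertion and tube-presence events in the group B scope of 7.4.1, and reconcile that paragraph with the adverse-event row of the schedule in 5.5, which covers both arms.
2. Record in the eCRF, for both arms, whether a feeding tube was in place at randomisation and the date and time of every tube placement. Enter tube status before the open-label assignment is known.
3. In 9.2.5, keep the comparison of all randomised patients, counted from randomisation, as the main AE and SAE comparison, and include patients whose insertion failed. Add a table of insertion-related events per patient, overall and by tube status at randomisation. Per-attempt counts belong there as description only, since the number of attempts arises after randomisation.
4. Do not rest the between-arm safety statement on post-placement events alone.

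The cost is a few fields taken from the chart and one or two tables. The subgroup without a tube at randomisation may be small, so its comparison will be imprecise and should be presented that way.

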1.8.2. Known potential benefits

Subject: smART Plus Comparative Study Protocol - Beilinson

As explained above, the various components of the smART+ System must operate as a cohesive system in order to allow feeding optimization as demonstrated in the flowchart below. With validation of the smART+ features during the study, the clinical benefit of the device will be the lowering of risks associated with tube displacement and malpositioning as well as lowering the risks associated with reflux and aspiration.

In addition, the smART+ System is able to continuously measure the patients REE and minimize the risk of overfeeding. Therefore, by reducing overfeeding it not only achieves feeding optimization, but it also reduces the likelihood of reflux episodes due to overfeeding.

2. Objectives and Endpoints

2.1. Primary Endpoint:

 ART MEDICAL PATIENT SAFETY TECHNOLOGY	Number: CRO-C-2822	Date issued: 01-Mar-2021
	Rev.06	Page 15 of 35

Subject: smART Plus Comparative Study Protocol - Beilinson

Optimization of the delivery of nutrition by the smART+ System as compared to standard of care, by automatically calculating and administering enteral feeding better than standard of care (REE or Calorimeter).

Optimization is defined as the ability of the system to provide adequate nutrition (not overfeed or underfeed) when compared to treatment via standard of care.

Evaluation will be conducted based on an analysis and comparison of the following parameters (obtained through the hospital's electronic records for control group and smART+ records for the treated group):

- Patient caloric target set
- Volume of patient nutritional intake value versus actual patient need – this is calculated by assessing the actual nutrition delivered, discarded nutrition in the GRV bags as well as the unused quantity in discarded feed bottles (if applicable).

As part of optimization evaluation, feeding efficiency calculation ((Net nutrition delivered [ml])/ (VTBD [ml])) should be calculated for the days when the patient received enteral feeding that given under medical order, removed from the patient, or stopped feeding that was not renewed until the end of the study. Feeding efficiency should not be calculated for the days that patient has been discontinued from enteral feeding by a medical order.

2.2. Secondary Endpoints:

- Safety

Safe use of the entire system will be assessed based on the occurrence of device related AE or SAE.

- Decrease in ICU length of stay.

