5.1. Divisions into Groups

After completion of the “initial screening” chapter in the study eCRF recruitment cycle, and after patient was found likely to participate in the trial, patients will randomly be divided into two groups.

Measures to minimize bias: randomization and blinding

Study participants will be randomly assigned to open-label study groups, in randomization ratio of 1:1.

In this current multicenter trial, the randomization procedures will be centrally organized. The ratio between treated and control groups should be balanced on each site.

In order to promote balanced allocation within the groups, the study randomization shall be stratified according to APACHE score measured at baseline.

To avoid possible bias in the selection and allocation of subjects and to ensure that the randomization is properly maintained throughout the trial, a computer randomization algorithm will be used for subject allocation to each group. The randomization algorithm will be part of the eCRF. Randomization will be implemented by the PI/Co-investigator after initial screening of the patient is completed (and before starting study procedures).

This will allow first of all the selection of suitable patients, and only then division into groups.

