7.3. Follow-Up

No follow-up will be conducted for this study. AE and SAE collection is to be conducted up until the moment the subject study participation is terminated. AEs and SAEs occurring after study termination are not to be collected or reported for the purpose of this study.

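### All adverse events are recorded on the device but only investigator-selected ones in control, so the between-arm any-AE test and by-arm AE tables partly compare recording rules

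*Combined protocol and SAP*

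**What the plan says.** Section 7.4.1 sets a different recording rule for each arm.

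- Group A: "All AEs occurring during the study must be documented appropriately regardless of relationship".
- Group B: "AEs recorded for group B should include only related or could affect (according to PI decision"), and the sentence goes on to confine these to conditions connected with urine, feeding, GRV and REE. It is ungrammatical, but on any reading it gives a subset chosen by the investigator.

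Section 5.1 confirms that whoever selects the events knows the arm: "Study participants will be randomly assigned to open-label study groups".

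Section 9.2.5 then treats the two arms as if they had been recorded alike. For tables: "AE data will be listed individually and summarized by SOC and by PT within a system organ class for each study group". For inference, a chi-square or Fisher's exact test is applied to the "difference in percent of subjects experienced any AE, drug-related AE and SAE between the study groups". Neither is limited to event types collected in both arms.

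The declared safety endpoint in section 2.2 is narrower: "Safe use of the entire system will be assessed based on the occurrence of device related AE or SAE".

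For SAEs the text is unclear. Section 7.4.2 says a "serious Adverse Event is an adverse event that" meets further criteria, so the group B restriction may carry over. But 7.4.2 makes no distinction between groups, section 7.3 gives a single rule ("AE and SAE collection is to be conducted up until the moment the subject study participation is terminated"), and the schedule in 5.5 marks adverse events for both arms at every stage.

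**The concern.** The group B rule can only remove events, and it does so in one arm. If the true event rates are equal, the recorded any-AE percentage is lower in control whenever some control patients have only events that fall outside the rule. The planned test can then report a significant excess on the device that the recording rule alone produced. A real reduction in overall AEs could be hidden in the same way. A reader of the by-arm tables could not separate the two causes.

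Two smaller points belong with this one.

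- 9.2.5 tests a drug-related AE category. There is no study drug, and 7.4.1 grades causality against the study device, which control patients do not have.
- 9.2.3 tests a between-group difference in the urine-flow assessment, which 2.2 builds on smART+ urine alerts. Group B has hospital urine and laboratory data (5.3.5) but no such alerts. In group A the UrineFlow module is used only as the investigator decides (5.2.2).

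**Working it through.** **Does anything else in the plan align the two rules?** No.

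- The schedule in 5.5 says when AEs are collected in each arm, not which ones.
- Section 7.3 says when collection stops, not what it covers.
- Section 7.4.3 lists anticipated events but does not widen the group B rule.

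**Size.** The plan states no AE rate, effect size or power for its safety tests, so there is no figure to reproduce. What follows is an illustration.

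Inputs from the plan:
- n = 100 per arm (3.1, 9.1).
- Two-sided significance at 5% (9.2.1).
- Chi-square or Fisher's exact test (9.2.5).

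Inputs assumed:
- True any-AE rate p, equal in both arms.
- Capture c, the share of group B patients with an AE who have at least one recorded.

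The recorded rates are then p in group A and p × c in group B. For recorded counts a and b, with m = (a + b)/(2n), the uncorrected chi-square statistic is

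X² = [(a − b)/n]² / [m(1 − m) × 2/n], significant when X² > 3.84.

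At the expected counts for p = 0.8, c = 0.75 (80 v 60): X² = 0.20² / (0.70 × 0.30 × 0.02) = 0.04 / 0.0042 = 9.52, significant. For p = 0.5, c = 0.75 (50 v 37.5): X² = 0.125² / (0.4375 × 0.5625 × 0.02) = 3.17, just short.

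The false-significance probability is the sum, over all 101 × 101 outcomes (a, b), of Binomial(a; n, p) × Binomial(b; n, pc) where the test rejects:

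| True rate p | Capture c | Recorded, A v B | Chi-square | Fisher |
|---|---|---|---|---|
| 50% | 100% | 50% v 50% | 5.6% | 4.0% |
| 50% | 90% | 50% v 45% | 11.8% | 9.2% |
| 50% | 75% | 50% v 37.5% | 44.4% | 38.8% |
| 50% | 60% | 50% v 30% | 83.2% | 79.2% |
| 80% | 100% | 80% v 80% | 5.1% | 3.3% |
| 80% | 90% | 80% v 72% | 26.2% | 21.2% |
| 80% | 75% | 80% v 60% | 88.0% | 84.4% |
| 80% | 60% | 80% v 48% | 99.8% | 99.7% |

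False significance reaches 50% at a capture of 0.730 (p = 50%) or 0.848 (p = 80%) by chi-square, and at 0.710 or 0.835 by Fisher.

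**The mild end of the range** (chi-square, p = 50%, 80%, 90%):
- 95% capture: 7%, 11%, 16%.
- 98% capture: 6%, 6%, 7%.

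**Masking.** Take assumed true rates of 60% on the device and 80% in control. The chi-square probability of a significant result in favour of the device is:
- 88.0% with equal recording (60% v 80%);
- 43.5% at 90% capture (60% v 72%);
- 2.6% at 75% capture, where both recorded rates are 60%.

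**The case against.** The best defence is that little rests on this test. The primary endpoint, ventilation days, length of stay and VAE do not use AE records, and the declared safety endpoint can be described from group A alone. The any-AE test is unpowered and supportive, and its bias runs against the device, so it cannot by itself give false reassurance. All of that stands, and it limits how far the problem reaches.

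The second argument is that capture may be high. One recorded event per patient is enough, the group B wording is broad, and section 7.4.2 expects a very large number of events in these patients. At 95 to 98% capture the any-AE test is only mildly disturbed, as shown above. This stands as a caution about size, but the documents do not establish that capture is that high. It would also rescue only the any-AE percentage: the SOC and PT tables would still list unrelated illness in the device column and screen it out of the control column.

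Third, the masking rates are invented, and reducing overall AEs is not a stated endpoint. That is fair; the example shows only that the distortion works in both directions.

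Fourth, bias in the SAE test is not established. That is also right. The text is ambiguous, and a clarifying sentence would settle it.

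**Conclusion.** The concern holds. Followed as written, the plan compares an unfiltered AE record on the device with an investigator-filtered one in control. The any-AE test and the by-arm AE tables are biased towards more events on the device, and nothing elsewhere in the protocol corrects this.

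The direction is certain and the size is not. It depends on the true AE rate and on group B capture, neither of which is given. Across the assumed range, false significance by chi-square runs from near nominal at almost complete capture to above 80% at 60% capture.

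The conclusion covers the any-AE test and the tables. The SAE test is exposed only if the group B restriction extends to SAEs. The device-related safety endpoint is unaffected. The between-group urine test is a separate fault: it has no control-arm counterpart for the smART+ alerts.

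**What to change.** Choose one of two routes.

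**(a) One rule.** Record AEs and SAEs in both arms under the same rule and in the same window, consent to end of participation. Section 7.4.1 states a start and stop for AE recording under the group A heading only, so the window should be written out for both arms. Cost: a protocol amendment, more eCRF entry in group B, and chart review for any control patients already enrolled.

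**(b) Keep the collection and change the analysis.** Remove the between-arm any-AE and SAE tests from 9.2.5. Report AEs descriptively by arm, with the two recording rules stated above each table. If a between-arm comparison is still wanted, confine it to a predefined list of objective events recorded identically in both arms without investigator selection. Cost: wording changes only, plus definitions and matching eCRF items if the list is used.

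Under either route:
- If the SAE test is kept, state in 7.4.2 that all SAEs are recorded in both arms.
- In 9.2.5, replace the drug-related category with device-related AEs, summarised in group A only with a 95% confidence interval.
- In 9.2.3, replace the between-group urine test with an estimate, within group A patients on UrineFlow, of how the alerts perform against laboratory results. Keep the usability summary.

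Neither route needs more patients.
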